9.2 SAMPLE SIZE DETERMINATION

Our study will include 50 subjects in each arm (i.e., 100 subjects in total), which is based on feasibility and availability of resources. However, if a formal power calculation were to be conducted using a two-sample t-test at a significance level of 0.05, a sample size of 100 subjects would be more than sufficient to detect a difference in mean blood loss of about 150 mL to 200 mL between the control group and the treatment group, which the investigators consider to be clinically significant. The table below shows different scenarios for higher and lower mean blood loss, as well as, scenarios with a larger standard deviation. The assumed pooled standard deviation derived from the study by Moo et al was 271.5 (the standard deviations of the control and bone wax groups in the study were 282.7 mL and 259.8 mL, respectively).

Mean Blood Loss POD 1 Difference (control - bone wax)	Pooled Std Dev	Power
153	271.5	80%
200	271.5	95%
175	300.0	82%
200	300.0	91%
200	350.0	81%

9.3 POPULATIONS FOR ANALYSES

All analysis will be conducted on the intention-to-treat (ITT) population. The ITT population is defined as all randomized participants analyzed in the group to which they were randomized, regardless of the treatment received.

9.4 STATISTICAL ANALYSES

9.4.1 GENERAL APPROACH

Descriptive statistics (mean, standard deviation, frequencies and percentages) will be used to describe the baseline clinical and demographic characteristics of the sample. The treatment and control groups will be compared using formal statistical tests on all other outcomes.

All analyses will be considered significant at $p < 0.05$ and conducted in SAS v. 9.4 (SAS Institute, Inc., Cary, NC).

9.4.2 ANALYSIS OF THE PRIMARY EFFICACY ENDPOINT(S)

Estimated total blood loss on POD 1 will be compared between the treatment and control groups using a two-sample t-test. If the standard assumptions of Normally distributed residuals and equality of variance do not hold, then an appropriate transformation or non-parametric method will be used.

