4 STUDY DESIGN

4.1 OVERALL DESIGN

- **A statement of the hypothesis:** The use of bone wax on exposed cancellous bone surfaces will provide superior hemostasis.
- **Phase of the trial:** NA. This study is using a FDA approved marketed product as per the package instructions.
- **A description of the type/design of trial to be conducted:** A prospective, randomized, single-blinded superiority study to evaluate bone wax use for hemostasis during primary unilateral total knee arthroplasty.
- **A description of methods to be used to minimize bias:** All patients scheduled for unilateral total knee arthroplasty will be approached for inclusion in the study.

- **The number of study groups/arms and study intervention duration:** This study will consist of 2 cohort groups. One group (50 patients) will have bone wax applied to the exposed cancellous surfaces of the bone (treatment group). The other group (50 patients) will serve as a control group. This study is a 1:1 allocation ratio. The patients will not be aware of their randomization assignment.
- **Indicate if single site or multi-site:** Single Site-Syosset Hospital Department of Orthopaedics
- **Name of study intervention(s):** Bone Wax
- **Note if interim analysis is planned and refer to details:** No interim analysis is planned.
- **Note if the study includes any stratifications:** Patient stratification is not needed for the randomization.
- **Name of sub-studies, if any, included in this protocol:** Not Applicable

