4.2 SCIENTIFIC RATIONALE FOR STUDY DESIGN

The investigators would like to address limitations in the studies done by Moo and Shin by conducting a prospective, randomized trial.

This study is designed to assess if applying bone wax to exposed cancellous bone during total knee arthroplasty provides superior hemostasis. Patients will be randomized to receive bone wax (treatment group) or no bone wax (control group). Blood loss will be calculated using the Hb-balance Formula to provide a consistent measurement of perioperative and postoperative bleeding. All other standard of care intraoperative blood minimizing strategies will be consistent for these patients. These strategies include pneumatic tourniquet, intravenous tranexamic acid, and spinal anesthesia. The Inclusion/Exclusion criteria were developed to ensure this consistency.

Objective and functional outcomes will be obtained using the 2011 Knee Society Score (KSS). The KSS will be completed preoperatively and postoperatively at the 8 week visit, or the visit closest to this time point., (Appendix B- Preoperative/Postoperative 2011 Knee Society Scores)

Preoperatively patients taking anticoagulants or antiplatelets, with the exception of aspirin 81 mg daily, will be excluded from the study as these medications could adversely affect intraoperative and postoperative bleeding. Patients with any bleeding dyscrasias will also be excluded from the study. Patients who are unable to stop these products for any reason will be excluded from the study.

Laboratory testing done as standard of care for all preoperative surgical patients are comprehensive metabolic panels and complete blood count. These laboratory values will be used to evaluate the inclusion and exclusion criteria for study enrollment. This study does not require any study specific laboratory tests.

On the operative day patients will be interviewed to confirm their agreement to continue in the study. Patients will be re-consented by [name] or [name] if the date of the original consent is greater than 30 days from the date of surgery. The inclusion and exclusion criteria will be verified prior to study randomization using the laboratory testing done in Pre-surgical Testing (PST) and the preoperative medical history documents. Patients will be randomized to either the treatment group (bone wax) or the control arm (no bone wax). The operating room (OR) staff will be notified of the treatment arm.

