Intraoperative blood management strategies will be consistent for all subjects to avoid any confounding factors which could affect postoperative transfusion requirements. Any patients unable to be treated according to the department treatment guidelines will be excluded from the study. Intraoperatively blood loss is minimized by anesthetic techniques, pharmacologic interventions, and surgical techniques, as per standard of care and department treatment guidelines.

The patient and the postoperative hospital staff will be blinded to the treatment arm. The OR staff will be trained not to discuss this information with the patient. During the transition of care from the OR to the Post Anesthetic Care Unit (PACU) the use of bone wax is not routinely included in the verbal patient report. The lack of this information is not required to effectively manage the patient in the postoperative period and will not affect patient care. Postoperatively medical care is managed by the hospitalist, medical doctors specializing in the care of hospitalized patients. Hgb and Hct are drawn daily during the patient's hospitalization as per the standard of care. These values will be used to calculate the Hb-balance Formula.

Blood loss will be calculated using the Hb-balance Formula. This method is being used to provide a more standardized method of calculating blood loss. Eipe and Ponniah showed that surgical blood loss was underestimated by 64% when clinical methods are used to assess blood-soaked sponges and blood lost to suction bottles and the vacuum drain.⁷

Following discharge patients will be followed in the outpatient surgical office according to the postoperative standard of care visit schedule. Results of the 2011 KSS Objective and Functional Outcome Measurements administered as part of standard of care at the 8 week postoperative visit, or the office visit closest to these time points will be collected for research purposes. Patients will be called at 56 days (+2weeks) from the date of surgery for any device related adverse events. This call is standard of care for the department. Three attempts will be made to reach the patient before they are considered "lost to follow-up".

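### The primary t-test of POD 1 blood loss uses no baseline covariates, although preoperative hemoglobin and demographics are already collected: an avoidable loss of precision, not a bias

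*Combined protocol and SAP*

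**What the plan says.** Section 9.4.2 gives the primary analysis: "Estimated total blood loss on POD 1 will be compared between the treatment and control groups using a two-sample t-test". If normality or equal variance fails, "then an appropriate transformation or non-parametric method will be used". Neither sentence names a covariate. Sections 9.4.7 (subgroups) and 9.4.9 (exploratory) are marked not applicable. ANCOVA appears only in the abbreviation list of Section 10.3, which describes itself as a template.

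The baseline data are collected anyway. Section 4.2 says: "Laboratory testing done as standard of care for all preoperative surgical patients are comprehensive metabolic panels and complete blood count". The schema in Section 1.2 lists baseline laboratory values, and the schedule in Section 1.3 lists demographics in the preoperative period. A preoperative hemoglobin threshold is an inclusion criterion in Section 5.1. The hemoglobin change from before surgery to POD 1 is a secondary endpoint, so preoperative values enter the secondary models of Section 9.4.3.

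On design, Section 4.1 states: "Patient stratification is not needed for the randomization". Section 9.2 sets 50 per arm, "which is based on feasibility and availability of resources", and illustrates power "using a two-sample t-test at a significance level of 0.05".

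**The concern.** In a randomized comparison of means, a baseline variable that predicts the outcome can be put in the model to remove the variation it explains. The plan holds such variables for every patient and does not use them for its primary comparison, nor does it say why.

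This matters because the number of patients was set by resources and three of the five power scenarios in Section 9.2 sit at 80 to 82%. No allowance for dropout is stated.

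Preoperative hemoglobin is a natural candidate because the endpoint comes from a hemoglobin balance. The formula is not written out, however. Section 4.2 ties only the daily inpatient values to it: "These values will be used to calculate the Hb-balance Formula". That the preoperative value is also an input is a reasonable inference, since a balance needs a starting point, but it is not a documented fact.

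What is at stake is a somewhat higher chance of missing a difference of 150 to 200 mL, which the investigators regard as clinically significant, and a wider confidence interval than the data require.

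**Working it through.** **Inputs.** From Section 9.2: n = 50 per arm, alpha 0.05, and five pairs of difference and SD. The SD of 271.5 mL follows from the two arm SDs quoted there: sqrt((282.7² + 259.8²)/2) = 271.49. Sidedness is not stated. The multiple correlation rho between the covariates and blood loss is not in the documents and is **assumed** over a range.

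**Step 1: reproduce the plan's table.** The noncentrality is d / (SD × sqrt(2/50)), with 98 degrees of freedom. For the first row, 153 / (271.5 × 0.2) = 2.818. A two-sided test then has 79.7% power against the stated 80%. The other rows give 95.4% (stated 95%), 82.3% (82%), 91.0% (91%) and 80.8% (81%). A one-sided test would give 87.6% in the first row, so the table is two-sided. The plan's figures are correct.

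**Step 2: adjust.** Residual SD = SD × sqrt(1 − rho²). For rho 0.5 this is 271.5 × 0.866 = 235.1 mL, and the noncentrality is 153 / (235.1 × 0.2) = 3.254. Results for 153 mL and SD 271.5 mL:

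| Assumed rho | Variance explained | Residual SD (mL) | Power, 97 df | Power with imbalance allowance, two covariates |
|---|---|---|---|---|
| 0 | 0 | 271.5 | 79.7% | 78.8% |
| 0.2 | 0.04 | 266.0 | 81.3% | 80.4% |
| 0.3 | 0.09 | 259.0 | 83.3% | 82.5% |
| 0.4 | 0.16 | 248.8 | 86.1% | 85.4% |
| 0.5 | 0.25 | 235.1 | 89.6% | 89.0% |

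The fourth column charges one degree of freedom; charging three changes it by at most 0.1 point. The last column is stricter. It uses 96 df and multiplies the residual SD by sqrt(1 + 2/95) = 1.0105, the average cost of chance covariate imbalance between arms. On that basis adjustment breaks even at rho of about 0.15 and costs under 1 point if rho is zero.

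**Step 3: the other rows** (97 df):

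| Difference / SD (mL) | Unadjusted | rho 0.3 | rho 0.5 |
|---|---|---|---|
| 175 / 300 | 82.3% | 85.7% | 91.5% |
| 200 / 350 | 80.8% | 84.3% | 90.4% |
| 200 / 300 | 91.0% | 93.3% | 96.8% |
| 200 / 271.5 | 95.4% | 96.9% | 98.8% |

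**Step 4: in patients.** Dividing 50 by (1 − rho²) gives the unadjusted size per arm with about the same power: 50/0.91 = 55 at rho 0.3, 50/0.84 = 60 at rho 0.4 and 50/0.75 = 67 at rho 0.5.

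**The case against.** The strongest reply is that nothing here is wrong. Under 1:1 randomization the unadjusted t-test is unbiased and keeps its type I error, and its standard error already reflects chance imbalance. It also matches the test behind the power table. All of that stands. A reader might infer from the unstratified randomization and the missing covariates that the wax effect would be biased; the documents do not support that.

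A second reply is that the size is unknown. This also stands. A reader might take the gain of about 10 points at rho 0.5 as what the plan loses. That figure needs the covariates to explain a quarter of the variance, and nothing in the documents shows that preoperative hemoglobin and sex do so. At rho 0.2 to 0.3 the gain is about 2 to 4 points, and scenarios already at 91% or 95% gain less.

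Third, a reader might say that a chance difference in preoperative hemoglobin passes straight into the estimated loss, by some number of mL per g/dL. Without the formula, neither the route nor the number can be stated. Likewise, estimated blood volume cannot be called already available: no section says it is calculated, and Section 1.3 does not list what demographics include.

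What remains is that the choice is lopsided. Adjustment costs almost nothing if the covariates are weak and helps if they are moderately predictive, and the plan gives no reason for leaving them out.

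**Conclusion.** The point holds as a matter of efficiency. The primary analysis makes no use of baseline information that the trial collects anyway, in a study that has fixed its size by feasibility. At the plan's 80% scenario, prespecified adjustment would take power from 79.7% to about 81%, 83%, 86% or 90% for an assumed multiple correlation of 0.2, 0.3, 0.4 or 0.5. These figures assume 50 analyzed patients per arm, a two-sided 0.05 test and the plan's own SD, and they rest on a correlation that the documents do not give. The role of preoperative hemoglobin in the formula is inferred.

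The evidence does not support calling the t-test invalid, calling the trial underpowered by the plan's own figures, or fixing the loss at a single number. Label: free improvement.

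**What to change.** In Section 9.4.2, before any unblinded data are seen, make the primary analysis a linear model (ANCOVA) of POD 1 estimated blood loss in mL on randomized arm, preoperative hemoglobin and sex. Add estimated blood volume only if the Hb-balance calculation proves to use it. Confirm that sex is among the demographics recorded. Report the adjusted mean difference in mL with its 95% CI, and keep the two-sample t-test as a supportive analysis. The sentence on assumptions would then refer to the residuals of this model.

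The cost is an amendment to the wording and slightly more analysis work. With preoperative hemoglobin and sex, no new patients, visits or laboratory tests are needed. The downside is two or three of 98 degrees of freedom, under 1 point of power with two covariates at the plan's 80% scenario if they prove useless, and a headline result that is an adjusted rather than a raw difference.

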9.4.3 ANALYSIS OF THE SECONDARY ENDPOINT(S)

Separate linear mixed models for repeated measures will be used to compare each secondary outcome of interest (hemoglobin, hematocrit and KSS) between the treatment and control groups over time from preoperative to postoperative. An appropriate transformation will be used for any outcome that does not meet standard assumptions of Normality.

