3 OBJECTIVES AND ENDPOINTS

OBJECTIVES	ENDPOINTS	JUSTIFICATION FOR ENDPOINTS

Primary
 
• Efficacy: To assess whether bone wax results in superior hemostasis in patients undergoing primary unilateral TKA• Safety: To compare the safety profile between the 2 cohorts	
• To calculate estimated perioperative blood loss on POD 1 using the Hb-balance Formula• To assess the patients for any device adverse events related to the use of bone wax	
Use of the Hb-balance Formula provides a more accurate assessment of blood loss
 
To ensure there are no safety issues between the two cohorts

Secondary	
• To assess whether objective and functional outcomes in patients undergoing primary unilateral TKA differ between the two patient cohorts• To determine if there is a difference in blood loss between the two cohorts 
• To calculate the Knee Society Scores, both objective and subjective scores, done preoperatively and 8 weeks postoperatively• To measure the difference between the preoperative and POD1 Hemoglobin (Hgb) and Hematocrit (Hct) values in the two patient cohorts	
The Knee Society Score is a validated tool to assess both objective and subjective outcomes. The collection of the KSS is a standard of care for Drs. [name] and [name]'s TKA patients.
 
These values will be used to assess hemostasis over time

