9 STATISTICAL CONSIDERATIONS

○ 9.1 STATISTICAL HYPOTHESES

- Primary Efficacy Endpoint(s):

The primary endpoint is estimated total blood loss measured on POD 1, as calculated by Hb-Balance formula. Blood loss is measured in the morning prior to receiving anticoagulant treatment. We hypothesize that applying bone wax during TKA will reduce blood loss on POD 1.

- Secondary Efficacy Endpoint(s):

The secondary endpoints are hemoglobin and hematocrit from preoperative to POD 1, as well as, the Knee Society Score (KSS), which is collected preoperatively and 8 weeks postoperatively. There are two KSS scores; namely, (1) the patient's self-assessment of pain, expectations and functional outcomes, as well as, (2) the surgeon's objective measurements.

We hypothesize that applying bone wax during TKA will reduce the quantity of change in hemoglobin and hematocrit from preoperative to POD 1.

We hypothesize that applying bone wax during TKA will positively impact KSS; namely, a reduction in pain, an increase in functional outcomes and an increase in alignment, range of motion and stability at 8 weeks postoperative.

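### Section 9.4.3 does not say how the preoperative value enters the secondary models or which contrast is tested; under the usual specification, precision on hemoglobin, hematocrit and KSS is left unused

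*Combined protocol and SAP*

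**What the plan says.** Section 9.4.3 reads: "Separate linear mixed models for repeated measures will be used to compare each secondary outcome of interest (hemoglobin, hematocrit and KSS", with the comparison made "between the treatment and control groups over time from preoperative to postoperative". Nothing further is given on fixed effects, covariance structure, covariates or the contrast to be tested. A transformation is allowed if Normality fails.

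The time points come from elsewhere. Section 3 defines the blood-count endpoint as "To measure the difference between the preoperative and POD1 Hemoglobin (Hgb) and Hematocrit (Hct) values in the two patient cohorts". Section 9.1 describes "the Knee Society Score (KSS), which is collected preoperatively and 8 weeks postoperatively" and distinguishes two KSS scores, one patient-reported and one measured by the surgeon. The Section 9.1 hypothesis for the blood counts is that bone wax "will reduce the quantity of change in hemoglobin and hematocrit from preoperative to POD 1"; the KSS hypothesis concerns the 8-week result.

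Section 9.4.1 sets the threshold: "All analyses will be considered significant at $p < 0.05$ and conducted in SAS v. 9.4". Section 9.2 gives the size: "Our study will include 50 subjects in each arm (i.e., 100 subjects in total". ANCOVA appears only in the abbreviation list of Section 10.3, which describes itself as belonging to a template, so it is not evidence of a planned adjustment.

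**The concern.** With a single postoperative value per endpoint, a repeated-measures model has something to repeat only if the preoperative value is one of the responses. The usual way to write such a model is arm, time and arm-by-time, which leaves the preoperative means of the two arms free to differ. The arm-by-time term is then the difference in mean change, with the preoperative value given a fixed weight of 1.

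Patients are randomized 1:1, so the two arms have the same expected preoperative mean. An analysis that uses this fact can estimate the best weight for the preoperative value instead of fixing it. It targets the same treatment effect.

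At stake is the width of the intervals for hemoglobin, hematocrit and the KSS scores. The plan states no power for any of these, and Section 9.2 says that the sample size was set by feasibility, so the analysis method is the main remaining route to precision. Section 2.2 also presents KSS collection as one of the ways in which this trial improves on earlier studies.

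**Working it through.** **Inputs from the documents.** 50 patients per arm (Section 9.2), 1:1 allocation (Section 4.1), significance at 0.05 (Section 9.4.1), and one preoperative and one postoperative value per secondary endpoint (Sections 3 and 9.1).

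**Inputs not in the documents, assumed here.** The preoperative-to-postoperative correlation rho, shown from 0.3 to 0.9. Equal standard deviations s at the two visits, relaxed below. An effect of 0.5 s, used only to illustrate power.

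**The plan's own figures.** The only power figures are for the primary t-test on blood loss. The noncentral t with 50 per arm and two-sided 0.05 gives 79.7%, 95.4%, 82.3%, 91.0% and 80.8%, against the stated 80%, 95%, 82%, 91% and 81%. The table reproduces and is two-sided. It has no counterpart for the secondary models.

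**Step 1: what the free-means model tests.** With two visits and complete data, the arm-by-time estimate is

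(post − pre, bone wax) − (post − pre, control),

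and its test is the two-sample t-test on change.

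**Step 2: variances with equal standard deviations.**
- Change contrast: 2(1 − rho) · s² · (2/n)
- ANCOVA (large sample): (1 − rho²) · s² · (2/n)
- Ratio, ANCOVA to change: (1 + rho)/2

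Worked case, rho 0.5 and n = 50 per arm. The change contrast has SE √(1.00 × 0.04) = 0.200 s. ANCOVA has SE √(0.75 × 0.04) = 0.173 s. For an effect of 0.5 s the noncentralities are 2.50 and 2.89, so power is 70% and 82%.

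| rho | ANCOVA / change variance | Variance saving | Extra SE of change contrast | Power, change | Power, ANCOVA |
|---|---|---|---|---|---|
| 0.3 | 0.65 | 35% | 24% | 55% | 74% |
| 0.5 | 0.75 | 25% | 15% | 70% | 82% |
| 0.7 | 0.85 | 15% | 8% | 89% | 93% |
| 0.8 | 0.90 | 10% | 5% | 97% | 98% |
| 0.9 | 0.95 | 5% | 3% | >99% | >99% |

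Put as sample size, 100 patients analysed by ANCOVA give the precision of 100/0.65 = 154, 100/0.75 = 133 and 100/0.85 = 118 patients analysed by change at rho 0.3, 0.5 and 0.7. At 0.8 and 0.9 the figures are 111 and 105.

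**Step 3: unequal standard deviations.** With s0 preoperatively and s1 postoperatively, the per-patient variances are s0² + s1² − 2·rho·s0·s1 for change and s1²(1 − rho²) for ANCOVA. The difference is (s0 − rho·s1)², which is never negative and is zero when s0/s1 = rho. Two examples of the change-to-ANCOVA ratio:
- s0/s1 = 0.8, rho 0.8: 0.36/0.36 = 1.00, so no gain.
- s0/s1 = 1.25, rho 0.5: 1.3125/0.75 = 1.75, against 1.33 with equal standard deviations.

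**Step 4: mixed model with a common preoperative mean.** In 4,000 simulated trials per rho (50 per arm, s = 1), the standard errors were:

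| rho | Free means, arm-by-time | Common preoperative mean | ANCOVA |
|---|---|---|---|
| 0.3 | 0.238 | 0.194 | 0.194 |
| 0.5 | 0.199 | 0.173 | 0.173 |
| 0.8 | 0.129 | 0.123 | 0.123 |

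The constrained model matches ANCOVA. The loss comes from leaving the preoperative means free, not from placing the preoperative value in the response.

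**The case against.** The best reply is that Section 9.4.3 never says the preoperative means are free. A reader might infer that modelling the preoperative value as an outcome throws precision away in itself. That is not so: with a common preoperative mean nothing is lost, and the text does not exclude this. Even the free-means contrast uses the preoperative value, only with a fixed weight. This stands, and it makes the loss conditional. It does not make the present wording adequate, because the constraint has to be written in deliberately and the usual specification omits it.

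A second tempting reading is that the arm main effect, averaged over both visits, would be tested. That would target half the postoperative effect, and at rho 0.5 power for an effect of 0.5 s would be about 30% (effect 0.25 s, SE √(0.75 × 0.04) = 0.173 s). The documents do not support this as the plan: Section 9.1 states its hypotheses as change to POD 1 and as the KSS result at 8 weeks. The contrast is unnamed, but this choice is unlikely.

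A third is that KSS would lose most. No correlation is given for KSS, hemoglobin or hematocrit, so the outcomes cannot be ranked.

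It is also fair to say that hemoglobin and hematocrit are drawn daily in hospital (Sections 1.3 and 4.2), so repeated measures is not an odd choice for them. The named endpoint is still the preoperative-to-POD 1 difference, which is two values. Finally, at rho 0.8 to 0.9 with equal standard deviations the gain is small.

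**Conclusion.** The point holds as a gap in specification with a conditional cost in precision. Under the usual free-means model the secondary tests are change-score t-tests. With equal standard deviations, ANCOVA has 35% to 5% less variance for rho from 0.3 to 0.9. These figures are not bounds, since rho and both standard deviations are assumed; the gain can be zero or exceed the range shown. That ANCOVA is never less precise is a large-sample result; with 50 per arm the one extra estimated slope costs little.

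No bias arises from the change contrast. The primary t-test and its power table are unaffected, and the plan claims no power for the secondary endpoints. This is a free improvement, not an error that threatens the trial's conclusions.

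**What to change.** Rewrite Section 9.4.3 so that, for hemoglobin, hematocrit and each KSS score separately, it specifies one of these:

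- ANCOVA of the postoperative value (POD 1 for hemoglobin and hematocrit, 8 weeks for KSS) on arm, with the preoperative value as covariate; or
- the mixed model with both visits in the response and the preoperative mean constrained equal across arms, that is, a time effect and an arm effect at the postoperative visit only, with an unstructured covariance.

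In either case, name the postoperative arm difference as the only tested contrast and report it with a 95% CI in the outcome's own units.

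The cost is a sentence or two of text and a small change to the SAS model statement. No new data, patients or procedures are needed. The choice should be fixed before outcome data are examined by arm.
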